3 INTRODUCTION, RATIONALE

Catheter ablation targeting the PVs and/or PV antrum has been recognized as the cornerstone of AF catheter ablation. But for non-PV sources of AF, ablation strategies remain controversial although several types of targets have been proposed: non-PV triggers, continuous fragmented atrial electrograms, ganglionated plexi, and linear lesions. Of note, in a recent multicenter trial, STAR AF-2, PV isolation (PVI) alone resulted in successful maintenance of SR in only 59% of patients with persistent AF.¹ This clearly reveals the need for establishing strategies to address non-PV sources of AF in non-paroxysmal AF. However, extensive atrial ablation lesion sets, such as ablation of CFAE sites or linear lesions, have not proven effective. In the STAR AF-2 trial, after 18 months, the freedom from recurrent AF in patients assigned to PVI alone (59%) was not improved by the addition of either CFAE ablation (49%) or linear ablation (46%), $p=0.15$.¹ Accordingly, PV isolation is now the most commonly performed procedure for not only paroxysmal AF, but also for persistent AF. However, there is little consensus as to what one should do beyond PV isolation.

Localized driver domains perpetuating AF have been difficult to detect with conventional techniques because of the limits of sequential temporospatial mapping, intermittent firing, and, presumably, spatial meandering of rotor-like activity. Accordingly, we propose to use a new software Computational Mapping Algorithm (CMA) that enables high resolution temporospatial mapping of atria for the identification of drivers of AF. CMA receives data from standard of care, commercially available 3D Mapping Systems (St. Jude Ensite System) and catheters and processes the data in a unique way. Electrogram and anatomy data are fed from the commercially available 3D Mapping

System to an adjacent laptop computer, via an Ethernet connection, that is running CMA. Commercially available 3D Mapping Systems track the position (X,Y,Z) of catheters and each electrode on the catheters in a 3D coordinate system. Further, these 3D Mapping Systems measure the electrical activity (electrograms) of the heart tissue with which each electrode comes in contact, much like an oscilloscope. These 3D Mapping Systems draw the position of the catheters in 3D on a computer screen to allow the physician to see their position without the use of ionizing radiation (x-ray). These 3D Mapping Systems then facilitate a process of “painting” the inside of a heart chamber with a catheter to create a cloud of X-Y-Z points that is used to create a 3D geometry (anatomic image) of the heart chamber. Concurrently, the 3D Mapping System is continuously displaying on the computer screen the electrograms measured on the electrodes, enabling the physician to see and diagnose arrhythmia within the context of the 3D geometry and the position of all the catheters.

The electrogram data and the 3D geometry data gathered by the 3D mapping system are passed to the laptop running CMA via an established communication protocol and an Ethernet cable. CMA then processes the electrogram data and generates a map of where the potential AF driver domains are located and superimposes those potential AF driver domain targets onto the 3D geometry of the anatomy (provided by the 3D mapping system). This AF driver domain map is displayed on the laptop computer that sits next to the 3D mapping system. This process is referred to as AF Mapping throughout the rest of this document. CMA employs a unique pattern recognition technology on electrograms recorded by a standard coronary sinus catheter to sequence and synchronize electrograms recorded throughout a particular atrial chamber of the heart with a standard spiral or loop catheter. CMA then stitches together electrograms panoramically throughout a particular atrial chamber, enabling the operator physician to visualize all the electrical activity of a particular chamber and thus identify drivers of AF. Further, CMA amalgamates and overlays physiologic data gathered by the standard catheters such as tissue voltage, enabling the physician operator to integrate information and holistically interrogate the patient’s condition to decide on a catheter ablation treatment strategy. This approach using CMA has the potential to reduce the amount of catheter ablation performed in a particular patient while focusing and targeting ablation on removing and/or isolating drivers of AF. This approach using CMA also has the potential to provide meaningful therapy options for patients with persistent AF that have undergone standard of care pulmonary vein isolation and still suffer from AF.

Extensive retrospective evaluation of CMA has been performed and published^{3,4}. A total of 70 patients have been mapped using CMA at Mercy Hospital in St. Louis, MO, University of Kansas Medical Center in Kansas City, KS, and Mount Sinai Hospital in New York, NY. No adverse events were associated with the mapping process. Fifty-five of the 70 mapped patients produced analysis that was usable. The unusable patient data can be attributed to initial tuning of the signal processing algorithms. In this 55 patient series of data, patients were mapped using CMA and subsequently ablated with standard of care ablation at the operator’s discretion, without the benefit of the CMA generated maps. Ablation techniques included Wide Area Circumferential Ablation (WACA), empiric Complex Fractionated Atrial Electrogram (CFAE) Ablation and empiric linear lesion Ablation. Retrospectively, the data was analyzed to see the effects of incidental ablation of CMA identified AF Driver domains. Ultimately, the use of CMA generated maps of AF driver domains may serve to reduce the amount of empiric CFAE and linear lesion ablation and improve outcomes in persistent AF patients.

The Abstract and Conclusion sections from the journal article entitled “***Characterization of Drivers in Patients with Persistent Atrial Fibrillation to Identify Substrate Based Rotor Ablation Targets***” serve as a good overview of CMA and associated retrospective clinical findings:

ABSTRACT: Recent clinical trials have shown that targeting rotors and focal impulses (FIs) during atrial fibrillation (AF) ablation improves outcomes. This study evaluated whether a novel computational mapping algorithm (CMA) could identify FIs and rotors, and characterize rotors when incidental ablation resulted in rhythm changes. Three-dimensional (3D) left atrial electroanatomic maps were created from signals recorded from multipolar circular mapping catheters in 61 patients undergoing persistent AF ablation. Forty of 61 acquired patient datasets were of adequate quality for analysis CMA, employing an AF pattern recognition algorithm, creating 3D panoramic AF maps identifying drivers of AF (FI and rotors) post procedure. Rotors were further classified as substrate (SBR) or non-substrate based (NSBR) on the basis of rotor stability, proximity to voltage transition zones and complex fractionated atrial electrograms (CFAEs). Incidentally ablated identified AF drivers, including SBRs and NSBRs, were evaluated for rhythm changes. A total of 172 drivers were identified in 40 patients (4.3 ± 2.2 drivers/patient). Seventy percent were rotors (120/172) and 30% were FIs (52/172). Sixty-seven percent of rotors were classified as SBR vs 33% as NSBR. Incidental ablation of SBRs resulted in rhythm change 91% of the time versus only 24% of the time for NSBR ($p < 0.0001$).

CONCLUSIONS: Incidental ablation of SBRs resulted in rhythm change significantly more frequently than ablation of NSBRs. Identification of drivers and classification of rotors based on substrate properties may allow a more tailored ablation approach in patients with persistent AF.

The following is a description of what each Mapping System will perform during Persistent Atrial Fibrillation cases:

St. Jude Ensite System:

1. Tracking the position of the catheters as they travel through the heart and displaying them on a screen in 3D so that X-Ray is not needed (or reduced).
2. Create a shell of the heart chamber and display on a screen so that the physician knows where the catheters are in relation to the anatomy (shell of heart chamber).
3. Display electrogram signals from all the electrodes on the different catheters in the heart.

These three features will be used for the entire case to determine where to ablate tissue.

AFTx System:

1. Receive the heart chamber shell from St Jude Ensite.
2. Receive the electrogram signals from St Jude Ensite.
3. Use proprietary software algorithms to create a map of where the potential sources causing AF are within the chamber and highlight them on the heart chamber shell.

The physician will then navigate a catheter to those highlighted areas (using St Jude Ensite) and further interrogate the areas for suspicious electrograms and decide if it is appropriate to ablate the tissue. Ultimately, St. Jude Ensite is the final tool used to decide whether to ablate or not.

5 SCHEDULE OF TREATMENT AND TESTS

TABLE 1: SCHEDULE OF TREATMENTS AND TESTS:

	Baseline	Procedure	Discharge	Event monitor 3 months	Event monitor 6 months	Event monitor 12 months
Type of visit	Office	Hospital		Office	Office	Office
Informed Consent	X					
Brief History & Physical	X			X	X	X
TTE	X					
EKG	X		X	X	X	X
1-wk Ambulatory Monitoring				X	X	X
Medications	X	X	X	X	X	X
Adverse Events		X	X	X	X	X

6 ENDPOINTS

6.1 Primary Endpoint

Primary Endpoints:	
1. Acute Procedural Outcomes as defined by termination of Atrial Fibrillation into NSR or AT > 5min.2. Clinical Outcome Analysis - Freedom from recurrent AF after one procedure at 12 months.3. Clinical outcome Analysis – Freedom from recurrent AF after two procedures at 12 months.
Additional Endpoints:	
1. Clinical outcome Analysis – Freedom from recurrent AT after one procedure at 12 months.2. Clinical outcome Analysis – Freedom from recurrent AT after two procedures at 12 months.3. Total duration of RF ablation/Fluoro time/exposure/procedure time4. Procedure-related adverse events5. Major Adverse Cardiac Events (MACE)6. Serious Adverse Events

7 STUDY SUBJECTS

7.1 INCLUSION CRITERIA

1. ≥ 18 years of age.
2. Patients are considered eligible if they have symptomatic or drug-refractory AF and are planned to undergo a catheter ablation procedure for persistent AF (either a first procedure or a redo procedure). Patients may have either persistent AF (AF > 7 days) or long-standing persistent AF (AF > 1 year's duration).
3. Ability to understand the requirements of the study and sign the informed consent form.
4. Willingness to adhere to study restrictions and comply with all post-procedural follow-up requirements
5. Projected lifespan greater than 1 year.

7.2 EXCLUSION CRITERIA

1. Rheumatic heart disease
2. Current intra-cardiac thrombus
3. History of MI or CABG within 6 weeks
4. Unstable angina
5. CVA or TIA within 3 months
6. Contraindication to anticoagulation
7. Class IV HF
8. Unable to sign consent
9. Projected lifespan of < 1 year
10. Women known to be pregnant or to have positive beta-HCG.
11. Participation in another study that would interfere with this study.

8 SAMPLE SIZE

This safety and efficacy study will enroll 65 patients across 1-5 US centers and 1-2 OUS centers. This number has been determined on the basis of study feasibility and not by statistical means. This is a feasibility study of the mapping system performance in which the sample size of the clinical investigation is intended to provide preliminary estimates of safety and performance.

The study will involve two cohorts. The first cohort will be composed of patients with persistent AF > 7 days but < 1 year's duration. The second cohort will be composed of up to 15 patients with long-standing persistent AF (AF > 1 year's duration).

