9.1 MAPPING COHORTS

In the first cohort of up to 15 patients, AF mapping (utilizing CMA) will be performed but will not be utilized to guide the ablation procedure. That is, ablation will be based on standard approaches only. The purpose of this initial cohort is to validate the software and mapping procedure. Brief operator learning curve relating to the mapping procedure is expected. Proper sampling is necessary in order to achieve full spatial coverage of an entire chamber. The benefit of the technology includes infinite spatial resolution with unlimited multiple synchronized sample locations throughout the atria, but that unlimited sampling must be balanced with time added to the procedure for sampling and software computation. The first cohort of patients is designed to allow for this learning curve to be normalized between the catheter operators and the software operators. Performing the mapping alone, Kurian T, et al. have seen no procedure related adverse events in over 61 patients. As such, it is safe and worthwhile to take an initial cohort of patients to normalize the mapping process in persistent AF patients where the chambers are often diseased, complex and dilated requiring operator skill to

sample an entire chamber appropriately. The consistent convergence of the CMA software within five minutes signifies that a balance has been struck between the amount of sampling data supplied to the software and the operator's satisfaction in adequate sampling of the patient's anatomy. Over the course of these cases, if the software algorithm is converging to a solution consistently within five minutes of processing time, the size of this validation cohort may be reduced to less than 15.

In the second cohort of patients (potentially patients 16-65), AF mapping (utilizing CMA) will be performed and used to point the operator to regions within a heart chamber that should be interrogated further for suspicious electrogram activity, as measured by the St. Jude Ensite System, and ablated if the suspicious electrogram activity persists.

➤ **Empiric ablation (CFAE or linear ablation) is not permitted**

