17 DATA ANALYSIS

This clinical study is a proof of concept study intended to assess the feasibility of the study mapping system. Baseline clinical characteristics (e.g. age, gender, renal function) and procedural characteristics (e.g. surface intracardiac electrogram and imaging findings) of the patients will be collected and analyzed.

Descriptive statistical data will be used to draw up the characteristics of subjects at the time of enrollment (demographics, baseline data). Quantitative parameters will be described using the following summary descriptive statistics: mean, standard deviation, median, and minimum and maximum values. Qualitative parameters will be described overall using frequencies and percentages. Percentages will be calculated on the number of non-missing observations. In all cases, the number of missing values will be specified.

Wilcoxon's test or Student's test for pairwise comparisons will be used, depending on the normality of the distribution, to study evolution in time.

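### Sections 8 and 9.1 use the same cohort labels for two different splits, and no endpoint is planned by either, so a single rate would mix guided with unguided patients and two AF-duration groups

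*Combined protocol and SAP*

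**What the plan says.** Section 8 gives the total: "This safety and efficacy study will enroll 65 patients across 1-5 US centers and 1-2 OUS centers". It adds: "This number has been determined on the basis of study feasibility and not by statistical means". It then splits the patients by AF duration. "The first cohort will be composed of patients with persistent AF" lasting more than 7 days but under a year, with no size stated. "The second cohort will be composed of up to 15 patients with long-standing persistent AF", meaning AF of more than a year.

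Section 9.1 splits by use of the map. "In the first cohort of up to 15 patients, AF mapping (utilizing CMA) will be performed", but ablation in these patients follows standard approaches only. Their purpose is to validate the software and settle the learning curve, and their number may fall below 15. The second cohort in that section is the remainder, provisionally numbers 16 to 65, in whom the map directs the operator.

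Section 7.1 states eligibility without a number: "Patients may have either persistent AF (AF > 7 days) or long-standing persistent AF". The Protocol Summary carries the same criterion.

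Section 6.1 lists three primary endpoints (acute termination of AF, and 12-month freedom from AF after one and after two procedures) and names no analysis population. The Protocol Summary ties the acute endpoint to all 65 patients, undivided. Section 17 is descriptive and assigns no outcome analysis to either split. Section 9 makes a patient a screen failure if no ablation resulted from the CMA map; the Protocol Summary gives only the 90-day screen-failure rule.

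**The concern.** The second cohort means at most 15 long-standing patients in section 8 and about 50 guided patients in section 9.1. The limit of 15 belongs to the second cohort in one section and to the first in the other. A table headed by cohort number could not be read without knowing which section it follows.

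The larger issue is the estimate. The study asks whether the map can find targets for ablation. Only the guided patients had ablation chosen with its help. With no stated population, the primary endpoints can be reported as one rate over everyone treated, which includes up to 15 patients in whom the map played no part. That rate also blends two AF-duration groups that section 8 set apart and section 17 does not use. In a single-arm study the reader has only this rate to judge by.

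**Working it through.** **Counts.** Section 8 gives 65 as a feasibility number, so there is no power or precision calculation to reproduce. Section 9.1 is consistent with it: 15 + (65 − 16 + 1) = 15 + 50 = 65.

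**The two splits side by side.**

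| Label | Section 8 (AF duration) | Section 9.1 (map use) |
|---|---|---|
| First cohort | > 7 days to < 1 year; 65 − 15 = 50 or more if the cap holds | up to 15, mapped but not guided |
| Second cohort | up to 15, > 1 year | about 50, guided |

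**Which denominator?** Counting everyone mapped and ablated gives 65. Applying the section 9 screen-failure rule literally removes the mapping-only patients, because none of their ablation results from the map. That leaves about 50. The documents support either.

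**Effect of AF-duration mix, cap held.** Let p be the rate in AF under a year, d the deficit in long-standing AF, m the number with long-standing AF and N the denominator. Then

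overall rate = p − d × m/N.

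Inputs: m = 15 (section 8) and N = 65 or 50. For illustration p = 59%, which section 3 cites for pulmonary vein isolation alone at 18 months in another trial. The documents give no rate by AF duration, so d = 10, 20 or 30 points is an assumption. The shift d × m/N does not depend on p.

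| d (assumed) | N = 65, m/N = 23.1% | N = 50, m/N = 30% |
|---|---|---|
| 10 points | 59 − 2.3 = 56.7% | 59 − 3 = 56% |
| 20 points | 59 − 4.6 = 54.4% | 59 − 6 = 53% |
| 30 points | 59 − 6.9 = 52.1% | 59 − 9 = 50% |

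**Effect of mixing in unguided patients.** The same formula applies with m = 15 mapping-only patients of 65. A difference of e points between guided and unguided patients moves the overall rate away from the guided rate by 0.231 × e: 2.3 to 6.9 points for an assumed e of 10 to 30, in either direction.

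**Effect of the missing link.** Suppose d = 20 and guidance has no effect. If all 15 long-standing patients fall in a mapping-only phase of 15, the phases read 39% (mapping-only) and 59% (guided). If all 15 fall in the guided phase, they read 59% and 53%. No phase comparison is planned, but a reader could make one.

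**Sampling error for scale.** The 95% Wald half-width is 1.96 × √(0.59 × 0.41/n): 12.0 points at n = 65, 13.6 at n = 50 and 24.9 at n = 15. Exact (Clopper-Pearson) intervals are 45.6% to 70.6% for 38/65, 45.2% to 73.6% for 30/50 and 32.3% to 83.7% for 9/15.

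**The case against.** Section 8 is protocol text in force. It holds long-standing AF to 15 of 65, and an enrolment quota need not be repeated among patient-level criteria: a patient can be eligible while the quota is full. Each section also defines its own groups, so neither is obscure where it stands. The labels do not alter who is enrolled. Within the cap, the shift from AF-duration mix is smaller than sampling error in a study that promises only preliminary estimates. AF type is recorded at baseline (section 10.1), so its share can be reported. All of this stands.

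It also rules out two stronger readings. A reader might infer from section 7.1 that the case mix is uncontrolled and could run from no long-standing patients to all 65. That requires ignoring section 8. The actual gap is that no one is assigned to track the cap across sites. A reader might also take "Qualitative parameters will be described overall using frequencies and percentages" as an instruction to pool the endpoints. That sentence belongs to the paragraph on characteristics at enrolment. Pooling of the 12-month endpoints is an inference from silence, and the Protocol Summary's mention of 65 for the acute endpoint could be read as timing rather than as a denominator.

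The objection does not supply an analysis population. Nor does being within sampling error remove the mixing: it is systematic, and a confidence interval around the mixed rate does not reflect it.

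**Conclusion.** The point holds as a gap in definition and reporting. Two unrelated splits share one set of labels, neither is used for any endpoint, and sections 8, 9 and 9.1 leave open whether the denominator is 65 or about 50. A rate over all 65 would include up to 23% unguided patients and so would not describe map-guided ablation.

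The size is modest. With the cap held, AF-duration mix accounts for about 2 to 7 points over 65 patients, or 3 to 9 points among 50, if the deficit in long-standing AF is 10 to 30 points. Those deficits and the 59% are illustrations, not trial assumptions. The absence of any link between the splits, and of the cap elsewhere, is confirmed only for the text available: some pages were removed and the figure in section 9 is not shown.

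**What to change.** - **Section 17.** Report each of the three primary endpoints for the guided phase as the main figure, with the mapping-only patients shown separately. Within the guided phase, report by AF duration using the section 8 groups (> 7 days to < 1 year; > 1 year), with exact 95% confidence intervals.
- **Sections 8, 9 and 9.1.** Reconcile them, including the screen-failure rule that read literally removes the mapping-only patients. Give the splits distinct names, for example AF-duration group and mapping phase.
- **Section 7.1 and Protocol Summary.** Cross-refer the existing cap of 15. Have the Data Coordinating Center track it across sites, and state whether a screen failure uses up a place, since patients count as enrolled at consent.

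The cost is wording and an extra split of tables already planned, with no new data. The main denominator drops from 65 to about 50, so the half-width grows from about 12 to about 14 points. A long-standing group of at most 15 gives about ±25 points, which supports description only.

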9 PATIENT ENROLLMENT AND WITHDRAWAL

Patients meeting the study inclusion criteria will be identified in the outpatient or inpatient setting by investigators. Patients will be followed by one of the study site principal or co-investigators.

The study will typically be described (including the risks and benefits) during the initial clinic or hospital visit. Consent will typically be obtained at the time of the initial assessment if it is clear that the patient truly understands the nature of the study. Alternatively, the patient will be encouraged to take a copy of the consent form home to contemplate whether he/she would like to be enrolled in the study. Only patients who voluntarily provide consent will be included in this study. Consent will be obtained prior to undergoing the ablation procedure. Patients will be able to withdraw from the study at any point without compromising their medical care. All data will be de-identified and protected in accordance with institutional and HIPAA guidelines, including 1) de-identification of all geographic subdivisions smaller than a state; 2) all elements of dates related to the individual; 3) telephone and fax numbers; 4) email addresses; 5) social security number, medical record, health plan beneficiary, account, and certificate/license numbers; 6) vehicle identifiers; 7) device identifiers; 8) URLs and IP addresses; 9) biometric identifiers; and 10) photographic images.

[figure not shown]
Eligible subjects will be consented for participation in the trial prior to undergoing AF ablation. Patients are considered enrolled once consented. Patients will be followed for 12 months. Patients who do not undergo an ablation procedure within 90 days of enrolling will be considered to be screen failures. Additionally, if a patient does not have any ablation performed that is a result of the mapping completed by the CMA software, the patient will be considered a screen failure. Patients who are deemed to be screen failures may be considered for re-enrollment should they require a later AF ablation procedure.

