10.3 PROCEDURAL DETAILS

- Patients will be brought to the electrophysiology laboratory in a fasting state
- Patients will undergo ECG to determine rhythm – i.e. Sinus rhythm v Atrial fibrillation
- Patients will undergo electrophysiology study using a mapping system and ablation as per standard practice. Placement of trimmed patches will be placed in standardized locations.
- The AF ablation procedure will be performed using any of the following marketed catheters: (Note: the first 3 catheters listed below are FDA approved for the treatment of paroxysmal

atrial fibrillation but not persistent The FlexAbility is only approved for treatment of typical atrial flutter.)

- Biosense-Webster Smart Touch SF
- Biosense-Webster Thermocool SF
- St. Jude Medical TactiCath Quartz
- St. Jude Therapy FlexAbility
- Intraprocedural anticoagulation will be administered with intravenous heparin, with target ACT levels ≥ 350 sec during any period in which catheters are positioned in the left atrium.
- For all patients, the initial ablation lesion set will consist of pulmonary vein isolation, assessed by entrance block during electrode recordings in the PV and by exit block during pacing from the PV.
- It will be suggested to operators that energy and duration of any RF lesions delivered either during PV isolation or subsequent ablation of drivers should be titrated to a goal tissue impedance drop ≥ 10 ohms from baseline during each lesion. Additionally, acute elimination of all local electrograms at ablation sites will be encouraged.

Presenting rhythm - Sinus

- AF is induced by pacing
- Electro anatomic maps of right and left atria are created and PV isolation is assessed with multielectrode mapping catheter.
- Once this occurs - **Map_{inducedAF}** is obtained using the CMA software running on the laptop adjacent to the 3D Mapping System.
- Ablation of drivers can be initiated in chamber with faster CL or with greater number of identified drivers
- Drivers can be addressed in order of importance as suggested by maps.
- Periodic reassessment of TCL in LAA and RAA to be done to help direct operator to chamber of interest- e.g. if there is significant gradient between RAA and LAA such that RAA is faster then drivers can be pursued in RAA prior to completion of all driver regions of LA

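### Patients can become screen failures after mapping and ablation, and no analysis set says whether they stay in the denominators

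*Combined protocol and SAP*

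**What the plan says.** Section 9 fixes entry at consent: "Patients are considered enrolled once consented. Patients will be followed for 12 months". It then gives two routes to screen failure. The first is administrative: no ablation within 90 days of enrolling. The second depends on what happens in the procedure: should a patient "not have any ablation performed that is a result of the mapping completed by the CMA software, the patient will be considered a screen failure". The section continues: "Patients who are deemed to be screen failures may be considered for re-enrollment should they require a later AF ablation procedure". The Enrollment row of the Protocol Summary carries only the 90-day route.

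Section 10.3 states: "For all patients, the initial ablation lesion set will consist of pulmonary vein isolation". Under Section 3 the physician takes the catheter to the highlighted areas to "further interrogate the areas for suspicious electrograms and decide if it is appropriate to ablate the tissue". Section 9.1 has two mapping groups. In the first, of up to 15 patients, the CMA map "will not be utilized to guide the ablation procedure". In the second, potentially patients 16 to 65, the map directs the operator to areas that are ablated only if suspicious activity persists.

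Section 6.1 gives the first primary endpoint as "Acute Procedural Outcomes as defined by termination of Atrial Fibrillation into NSR or AT > 5min". The other two are freedom from recurrent AF at 12 months, after one and after two procedures. Section 8 says the sample size is "intended to provide preliminary estimates of safety and performance". Section 17 defines no analysis set; its only denominator rule is that percentages use non-missing observations.

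**The concern.** Screening normally ends before the study intervention begins. Here the label can be applied to someone who has consented, been mapped with the investigational software and had pulmonary vein isolation. Whether it applies turns on the output of the software under study and on the operator's response to it.

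If such patients leave the analysis, the retained guided group is selected on a result of the procedure. Maps that led to no ablation would go uncounted, although Section 8 presents the trial as a feasibility study of how the mapping system performs. The endpoints do not need this restriction: the acute endpoint is AF termination, with no condition that a CMA-identified site was ablated. The plan tests no hypothesis on these endpoints, so the estimated rates are the product, and a rate has no clear meaning until its denominator is fixed.

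**Working it through.** **1. When the status becomes known.** Enrolment is at consent (Section 9). Mapping and pulmonary vein isolation follow (Section 10.3). Whether any ablation resulted from the map is known only during or after that procedure. The documents foresee patients without it: Section 10.3 (sinus presenting rhythm) covers the case in which no driver is localised, and Sections 3 and 9.1 leave ablation of a highlighted area to the operator's reading of the electrograms.

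**2. What the documents say about keeping these patients.**

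| Place | Leans towards | Why it does not settle the matter |
|---|---|---|
| Protocol Summary, Primary Endpoints | Keeping: ties the acute analysis to procedures on 65 patients | Can be read as timing; silent on whether screen failures count or are replaced |
| Section 5, Table 1 | Keeping: adverse events from procedure to 12 months, no exception | Does not mention screen failures |
| Section 9, 12-month follow-up | Keeping | Does not say it continues after relabelling |
| Section 13.1, one screening/enrollment series 001 to 065 | Keeping: a screen failure seems to use a number | The number follows a site prefix; replacement is not addressed |
| Section 13.4 | Keeping: withdrawal only by the subject's choice, or by the investigator for safety or compliance | Screen failure is neither, and its consequence is not stated |
| Section 9, the term itself and re-enrolment | Leaving | Never defined for analysis |
| Section 17 | Neither | No analysis set |

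A figure in Section 9 is not visible in the text available, so nothing is inferred from it.

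**3. Size, as an illustration.** The planned 65 was set by feasibility (Section 8), so there is no calculation to reproduce. If the validation group is the full 15, the guided group is 65 − 15 = 50. Let k guided patients be removed and s of the 50 − k kept be successes. Both k and a success rate near 60% are assumptions; the documents give neither.

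- Reported rate: s/(50 − k)
- Lowest possible rate in all 50 (every removed patient fails): s/50
- Highest possible rate in all 50 (every removed patient succeeds): (s + k)/50
- Width: k/50, or 2 percentage points per patient removed

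| k | Reported | Lowest | Highest | Exact 95% CI of reported rate |
|---|---|---|---|---|
| 5 | 27/45 = 60.0% | 27/50 = 54.0% | 32/50 = 64.0% | 44.3% to 74.3% |
| 10 | 24/40 = 60.0% | 24/50 = 48.0% | 34/50 = 68.0% | 43.3% to 75.1% |

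The bounds assume nothing about the removed patients' outcomes. In both rows they lie inside the Clopper-Pearson interval of the reported rate.

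**The case against.** The strongest reply is that exclusion is inferred, not stated. Patients count as enrolled at consent, so the protocol's screen failures are already enrolled and the term does not carry its ordinary sense. The places tabulated above lean towards keeping them. This stands: what is established is an undefined denominator, not a biased one.

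Four stronger readings are tempting and are not supported.

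- *The rule removes the whole validation group, leaving at most 50 countable patients.* Taken literally it would. But Section 9.1 expressly gives these patients standard ablation only and numbers the guided patients from 16, so they evidently count. An exemption should be written; its absence does not show an intention to remove them.
- *Late adverse events will be lost.* Table 1 and the 12-month follow-up make no exception for screen failures. The plan only fails to confirm that they apply.
- *Everyone caught by the rule has been mapped.* It also catches patients ablated without CMA mapping being started or completed.
- *Earlier series predict the share removed.* Section 3 reports 15 of 70 patients without usable analysis and 21 of 61 datasets of inadequate quality. These describe data quality, not absence of map-derived ablation, and Section 3 attributes the 15 to initial algorithm tuning. They are not forecasts.

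A sponsor may also say that CMA-ablated patients are a legitimate proof-of-concept population. They are, provided the set is labelled as such and shown beside the full group. Mapping yield is not a listed endpoint, so the plan does not misreport it.

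**Conclusion.** The point holds as a gap that should be fixed. Section 9 contains a rule that can relabel treated patients according to the map and the operator's decision, and no text says whether they remain in the efficacy and safety denominators. If the ordinary meaning is applied at analysis, the primary endpoints describe only patients whose map led to ablation.

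The size cannot be derived from the documents, and the direction of any bias is unknown. The bounds of 54% to 64% (5 removed) and 48% to 68% (10 removed) rest on an assumed number removed, an assumed rate near 60% and a guided group of 50. They are worst and best cases. That they fall within sampling uncertainty limits the practical effect in a feasibility study, but a confidence interval on the retained patients does not account for selection. A reader might infer that the trial is set to report an inflated success rate; the documents do not support that.

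**What to change.** - In Section 9, limit screen failure to patients who leave before CMA mapping starts, including those with no procedure within 90 days. Align the Protocol Summary.
- In Section 17, keep every patient in whom CMA mapping was started in the safety analysis, and apply to them the 12-month follow-up that Section 9 already states.
- Use all mapped patients of the guided group as the denominator for the acute and 12-month endpoints. Show the CMA-ablated patients as a labelled subset.
- Report how many mapped guided patients had no CMA-derived ablation, and why (unusable map, no driver localised, operator decision).
- State in Section 9.1 that the unguided validation group is not subject to the rule and is reported separately.
- Link any re-enrolled patient to the first record so that no one is counted twice.

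The cost is protocol wording, one or two data fields (map usability, reason for no CMA ablation) and follow-up of the retained patients, whose number is unknown. The reported rate may be less favourable. Nothing in the clinical conduct of the procedure changes.
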